## Introduction

Dental implants have revolutionized modern dentistry by providing a reliable and long-lasting solution for the replacement of missing teeth. A crucial factor in the success of dental implants, particularly in the posterior regions of the mandible, is the promotion of optimal bone and soft tissue healing.

Various biomaterials have been developed and tested to enhance osseointegration, accelerate healing, and improve long-term outcomes of implants. One such biomaterial that has gained considerable attention is platelet-rich fibrin (PRF), an autologous blood product known for its regenerative potential.

Platelet-rich fibrin (PRF) was initially introduced by Choukroun et al, 2006. Platelet-rich fibrin is a second-generation platelet concentrate that emerged as an improvement over platelet-rich plasma (PRP), offering several benefits such as the release of growth factors that promote tissue regeneration and wound healing. Unlike PRP, PRF is free of anticoagulants or additives, making it a purely autologous material. It is prepared by centrifugation of the patient's blood, which separates the blood components and yields a fibrin clot rich in platelets, leukocytes, and growth factors. PRF has been widely used in dental and medical fields, particularly in oral surgery, periodontology, and implantology, due to its ability to promote soft and hard tissue healing.

However, despite its success, Platelet-rich fibrin (PRF) has limitations, such as its short-lived release of growth factors and limited structural integrity, which has spurred the development of advanced forms of PRF. Advanced PRF (A-PRF), a newer variation, is produced using a slower and longer centrifugation process, which results in a higher concentration of leukocytes and platelets and a more extended release of growth factors.

This modification aims to enhance the regenerative potential of PRF, making it more suitable for complex procedures like immediate implant placements. especially in regions like the posterior area of the mandible, where healing can be challenging due to anatomical and biomechanical factors.

Immediate implant placement, where the implant is placed directly into the extraction socket following tooth removal, has become a common practice due to its potential to reduce treatment time and prevent alveolar bone resorption. However, the success of immediate implants depends heavily on the proper management of the extraction socket, which often requires the use of grafting materials to fill the gap between the implant and the socket walls and to promote bone regeneration.

Both PRF and A-PRF have been proposed as suitable filling materials for this purpose, but there is limited clinical evidence comparing their efficacy in terms of bone and soft tissue healing, particularly in challenging areas such as the posterior regions.

The posterior region of the jaw presents unique challenges for implant placement due to several factors, including reduced bone quality and quantity, increased masticatory forces, and the proximity of vital anatomical structures such as the inferior alveolar nerve. The success of implants in these regions is contingent on the rapid formation of new bone around the implant to ensure primary stability and long-term osseointegration.

PRF, with its regenerative properties, has been shown to aid in this process, but it remains unclear whether the newer A-PRF offers significant clinical advantages over PRF.

The key differences between traditional platelet-rich fibrin (PRF) and advanced platelet-rich fibrin (A-PRF) lie in the processing protocols, particularly in the centrifugation speed and time. PRF is typically obtained by centrifuging blood at a relatively high speed (around 2,700-3,000 revolutions per minute or RPM) for a short duration, usually 8-12 minutes. This results in a fibrin clot that contains platelets, leukocytes, and a network of growth factors. However, this method yields a more compact clot with a relatively rapid release of growth factors (7-14 days), leading to a shorter duration of biological activity.

In contrast, A-PRF is produced using a lower centrifugation speed (about 1,300-1,500 RPM) and a longer centrifugation time, ranging from 10-14 minutes. This slower and prolonged process allows for the collection of a PRF matrix that is more porous and contains a higher concentration of leukocytes and platelets. The altered centrifugation protocol of A-PRF results in a more homogenous distribution of cells and a slower, more sustained release of growth factors (10-28 days) such as transforming growth factor-beta (TGF- $\beta$ ), vascular endothelial growth factor (VEGF), and platelet-derived growth factor (PDGF). These factors contribute to enhanced angiogenesis, tissue regeneration, and a prolonged healing response, making A-PRF potentially more effective in promoting both soft tissue and bone regeneration compared to PRF.

### ***Aim of the Study:***

The aim of the study is a clinical and radiographic comparison between advanced platelet rich fibrin versus platelet rich fibrin as a gap filling material in immediate implant placement.

## Materials and Methods

### Study setting:

This study will be conducted on (16) patients in the outpatient clinic of Oral and Maxillofacial Surgery department, Faculty of Oral and Dental Medicine, Delta University for Science and Technology. The selected patients has a badly decayed mandibular posterior teeth which needs to be extracted and require teeth replacement by dental implant. The selected patients will undergo immediate dental implant placement and platelet rich fibrin or advanced platelet rich fibrin will be used as a filling material in the jumping gap.

### Criteria for patients' selection

#### • Inclusion criteria

- 1- The selected patients has a badly decayed mandibular posterior teeth which needs to be extracted and require teeth replacement by dental implant.
- 2- Healthy patients who are classified according to the American Society of Anesthesiologists (ASA)(2022) physical status classification as class I.
- 3- Patient aged between 25 and 60 years old.
- 4- Surgical site with initial alveolar ridge width range between (4-6 mm).
- 5- Sufficient interocclusal space (6-9 mm)
- 6- Adequate healthy gingival tissue.
- 7- Good oral hygiene.
- 8- Willing to complete the study.

#### • Exclusion criteria

- 1- Presence of any systemic condition affecting wound healing and success of procedures.
- 2- History of alcohol or drug dependency. psychological factor that might affect the surgical or prosthodontic treatment.
- 3- Non-Smokers.
- 4- Head and neck radiation treatment.
- 5- Severe bruxism or clenching habits.
- 6- Active periodontal diseases and periapical lesions not chronic infections.

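### Exclusion item 3 bars non-smokers, so as written the trial can enrol only smokers, which the protocol nowhere explains

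*Protocol*

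**What the plan says.** The protocol's section on patient selection has two numbered lists. In the second, headed "Exclusion criteria", items 3 and 4 read "3- Non-Smokers. - 4- Head and neck radiation treatment". Item 3 carries no qualifier, definition or reason.

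The items around it point the other way. Exclusion item 1 removes patients with "Presence of any systemic condition affecting wound healing and success of procedures". Item 2 removes patients with alcohol or drug dependency, or a "psychological factor that might affect the surgical or prosthodontic treatment". Inclusion item 2 asks for "Healthy patients who are classified according to the American Society of Anesthesiologists (ASA)(2022) physical status classification as class I", and inclusion items 6 and 7 require sound gingiva and good oral hygiene. The inclusion list has no entry on smoking.

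The aim is a "clinical and radiographic comparison between advanced platelet rich fibrin versus platelet rich fibrin as a gap filling material in immediate implant placement". The study setting describes the patients by their dental need: "The selected patients has a badly decayed mandibular posterior teeth which needs to be extracted and require teeth replacement by dental implant". Neither mentions smoking.

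**The concern.** An exclusion list names the people who may not enter. With non-smokers on it, only smokers are eligible. A trial of platelet concentrates in smokers is possible, but a protocol that intended one would be expected to say so and give a reason. This one does neither.

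Eligibility is an operative rule, applied to each patient at screening. Followed literally, it makes the result a statement about smokers, although the rest of the plan is written without that restriction. If staff silently reverse it, each non-smoker they enrol is a recorded eligibility violation. Analysis cannot repair this afterwards: with all patients in one smoking category, the data hold no information about the other.

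**Working it through.** This is mainly a check of the text.

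**1. Where smoking appears.** Exclusion item 3 is the only mention. The introduction, aim, setting, inclusion list, sample size, design, randomization, evaluation and statistical sections do not refer to it.

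**2. Whether the item could be an artefact of text extraction.** This is unlikely. It stands in sequence as item 3 of 6 under a clear heading.

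**3. Direction of the eligibility items.**

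| Item | What it does |
|---|---|
| Inclusion 2 | admits healthy ASA class I patients |
| Inclusion 6 and 7 | admit patients with healthy gingiva and good oral hygiene |
| Exclusion 1 | removes systemic conditions that affect healing |
| Exclusion 2 | removes dependency and psychological factors that affect treatment |
| Exclusion 3 | removes people who do **not** smoke |
| Exclusion 4 | removes patients with head and neck radiation |
| Exclusion 5 | removes severe bruxism or clenching |
| Exclusion 6 | removes active periodontal disease and certain periapical lesions |

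Item 3 is the only exclusion that refuses a patient for lacking a habit. Every other exclusion names an adverse condition, history or habit.

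**4. Possible populations, with 16 patients at 8 per arm.**

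- Item as written: 16 of 16 smokers.
- Item reversed, or moved to the inclusion list: 0 of 16 smokers.
- Item deleted: a mixture that the protocol does not fix.

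The first two populations do not overlap.

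**5. Whether the sample size depends on the item.** The inputs come from the Sample size section: 1.56 ± 0.52 and 0.69 ± 0.32, two-sided alpha 0.05, power 95%.

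- Pooled SD = √[(0.52² + 0.32²)/2] = √[(0.2704 + 0.1024)/2] = √0.1864 = 0.4317.
- d = (1.56 − 0.69)/0.4317 = 0.87/0.4317 = 2.015, against the stated 2.02.
- Two-sample t-test, noncentral t, d = 2.015: power is 93.2% at 7 per arm and 96.3% at 8 per arm.

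Eight per arm is therefore the smallest size that reaches 95%, and the stated total of 16 is reproduced. No input refers to smoking, so rewording item 3 does not alter this calculation.

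**6. Whether the comparison between arms is biased.** It is not. The Randomization section allocates by lottery, so any imbalance in smoking would be due to chance.

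**The case against.** The strongest reply is that this is a one-word slip in a 16-patient trial at a single clinic. Staff would read it in line with the rest of the list, and nothing shows that anyone has applied it literally. That argues for a lower rating, but it does not make the text right. The protocol gives nothing to correct the item against: no inclusion entry on smoking, no rationale and no definition. Staff would have to guess, and acting on the guess would breach a written criterion.

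Three narrower objections have force.

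- **Silence in the aim and setting is weak evidence.** Neither mentions the age range, ASA class or ridge width either, and all of those are real restrictions. The argument rests on the mismatch with the neighbouring criteria and on the missing explanation.
- **There is no strict contradiction.** The protocol does not say that smoking impairs healing or conflicts with ASA class I. The clash is one of apparent intent.
- **The sample size check shows little.** The protocol does not name the outcome, source or population behind its means and SDs. Whether they suit smokers, non-smokers or a mixture cannot be told. The check shows only that the calculation as stated does not involve smoking.

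**Conclusion.** The concern holds, and the item must be corrected before screening. As written, exclusion item 3 restricts the trial to smokers, without explanation and against the direction of the other criteria. It governs the eligibility of all 16 patients and sets the population to which the result applies. It does not affect the validity of the randomised comparison within whoever is enrolled, or the arithmetic behind the total of 16.

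Two assumptions are involved. One is that no smokers-only population is stated in pages not available for this review. The other is that the item is a slip, which is an inference from the surrounding list. The need for correction does not depend on the second: if smokers really are the target, the protocol still fails to say so where it describes its population.

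**What to change.** The sponsor should state the intended smoking rule and reconcile item 3 with both lists before anyone is screened. The document does not settle which rule was meant, so the choice is the sponsor's:

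- if smokers are to be kept out, correct item 3, or move the entry to the inclusion list;
- if smokers are the target, say so in the aim and add a matching inclusion item;
- if smoking is not meant to affect eligibility, delete the item.

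If screening has already begun under the present wording, check the smoking status of those screened once against the corrected rule. Reporting smoking status by arm at baseline would then be useful.

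The cost is one corrected line, or one sentence and one inclusion item. If screening has begun, add the one-time check and one row in the baseline table. The correction itself calls for no extra patients or visits.

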### Sample size:

Using G power program version 3.1.9.7 to calculate sample size based on expected effect size of 2.02 (  $1.56 \pm 0.52$  &  $0.69 \pm 0.32$  ) depending ,using 2-tailed test ,  $\alpha$  error =0.05 and power = 95.0% , the total calculated sample size will be 16 divided into two groups.

## **Study Design:**

For the study production the total number of the included patients will be 16 with respect to the inclusion criteria that is selected, patients will be randomly divided into two equal groups A&B, both of them will under-go Immediate implant placement each group will have its unique method of Filling up the jumping gap around the dental implant either by the use of Platelet-rich fibrin (PRF) or Advanced platelet-rich fibrin (A-PRF).

**Group A:** The jumping gap will be filled with Platelet-rich fibrin (PRF).

**Group B:** The jumping gap will be filled with Advanced platelet-rich fibrin (A-PRF).

## **Randomization:**

Each patient will be joined either to group A or B immediately after tooth extraction procedure through a random lottery mechanism (a startup number of 16 pre-printed paper for the first patient lottery, half of them with Platelet-rich fibrin (PRF) and the other with Advanced platelet-rich fibrin (A-PRF) with a probability of 50%) and the offending patient will choose the pre-printed paper with the specific procedure randomly and blindly.

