## **Surgical Procedures:**

After administration of Local anesthesia, gentle atraumatic extraction is performed for the nonrestorable tooth, followed by careful cleaning of the extraction socket. Drilling for the implant begins to create the correct depth and diameter for implant placement. The implant is installed according to manufactures instructions, ensuring proper seating and stability to promote integration with the surrounding bone.

**For Group A,** PRF preparation involves collecting 20 mL of venous blood into anticoagulant-free tubes, followed by centrifugation at 2,700-3,000 RPM for 8-12 minutes. This process separates the blood into layers, from which the fibrin clot is carefully extracted.

**For Group B,** A-PRF is prepared similarly but centrifuged at a lower speed (1300-1500 RPM) for 12-14 minutes to yield a higher concentration of platelets and leukocytes. After preparation.

PRF and A-PRF are applied to the implant site to aid tissue regeneration and integration. Application of Gelatin Sponge to cover the implant before suturing over the implant.

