## **Evaluation:**

### **1) Clinical evaluation:**

#### **A) Implant Stability:**

Implant stability will be measured by Resonance Frequency Analysis (RFA) ISQ unit at 3 months and 6 months post-operative .

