#### **B) Insertion torque:**

**Measurement Tools:** A torque wrench is used to measure the insertion torque during implant placement.

**Torque Values:** Generally, insertion torque values between 25-45 N/cm are considered optimal for primary stability. Lower torque values may indicate insufficient primary stability, while excessively high values (over 50 N/cm) could cause excessive stress on the surrounding bone.

**Comparative Analysis:** Compare the insertion torque values between the PRF and A-PRF groups to evaluate whether one preparation method offers superior initial stability, potentially affecting long-term outcomes.

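### Insertion torque is taken before any filler is in place, so it cannot show that one preparation gives better initial stability; drawing the arm before drilling is a secondary weakness

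*Protocol*

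**What the plan says.** All references are to the protocol.

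- **Study Design:** both groups have immediate implant placement, and "each group will have its unique method of Filling up the jumping gap around the dental implant". The filler, PRF or A-PRF, is the only planned difference.
- **Surgical Procedures:** after extraction and socket cleaning, "Drilling for the implant begins to create the correct depth and diameter for implant placement". Then "The implant is installed according to manufactures instructions, ensuring proper seating and stability". The two preparations are described after that, followed by "PRF and A-PRF are applied to the implant site to aid tissue regeneration and integration".
- **Evaluation, B) Insertion torque:** "A torque wrench is used to measure the insertion torque during implant placement". Its paragraph on comparative analysis then asks for torque to be compared between the PRF and A-PRF groups, to judge whether either preparation is better for initial stability. It adds that this may bear on later results.
- **Randomization:** "Each patient will be joined either to group A or B immediately after tooth extraction procedure through a random lottery mechanism". The patient "will choose the pre-printed paper with the specific procedure randomly and blindly". The paper thus carries the treatment name and not a code.
- **Evaluation, A) Implant Stability:** "Implant stability will be measured by Resonance Frequency Analysis (RFA) ISQ unit at 3 months and 6 months post-operative".

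**The concern.** The Insertion torque section treats a measurement made before the treatment as if it were a response to the treatment. If the groups happened to differ in torque, the trial would be set up to read that as an advantage of one preparation in primary stability, and to link it to later outcomes. The order of events rules out that causal reading.

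The time of the draw adds a second, weaker worry. Randomisation balances what precedes the draw; it does not protect steps carried out afterwards by someone who knows the arm. Here the arm is named before drilling and seating, which depend on the operator. A difference in placement could show in torque and might carry into ISQ at 3 and 6 months.

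**Working it through.** **1. Order of events.** Putting Randomization, Surgical Procedures and Insertion torque together gives:

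| Step | Event | Arm named? | Filler in place? |
|---|---|---|---|
| 1 | Extraction | no | no |
| 2 | Paper drawn | yes | no |
| 3 | Drilling | yes | no |
| 4 | Implant seated, torque recorded | yes | no |
| 5 | PRF or A-PRF applied | yes | yes |
| 6 | ISQ at 3 and 6 months | yes | yes |

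Socket cleaning falls between steps 1 and 3. Torque (step 4) comes before the filler (step 5). Study Design supports this order independently of the listing, because a gap around an implant exists only once the implant is there. So the filler cannot cause a difference at step 4. What remains is chance, or conduct between steps 2 and 4.

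**2. The plan's own figure.** Sample size gives means and SDs of 1.56 (0.52) and 0.69 (0.32), two-sided alpha 0.05, power 95% and 16 patients.

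- Pooled SD = sqrt((0.52² + 0.32²)/2) = 0.432.
- d = (1.56 − 0.69)/0.432 = 2.015, against 2.02 stated.
- Exact t-test power at d = 2.02 is 93.4% with 7 per arm and 96.3% with 8 per arm, so 8 per arm is the smallest size reaching 95%.

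The figure of 16 reproduces and does not bear on this point.

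**3. A chance difference in torque.** With 8 + 8 patients, df = 14 and the two-sided 5% critical t is 2.145. The smallest observed gap reaching p<0.05 is 2.145 × sqrt(2/8) = 2.145 × 0.5 = 1.07 SD. With no real difference this occurs in 5% of trials (5.03% in 200,000 simulated trials). That is simply alpha. What is particular here is that any such result would be a false attribution, since the filler has no route to torque.

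**4. How often the arm could be known before torque.** With the draw as written, up to 16 of 16 patients. With the draw after torque, only when all remaining papers are of one kind. For 8 + 8 papers drawn without return, the expected number of such patients is 8/9 + 8/9 = 16/9 = 1.8. This assumes that papers are not put back (the likelier reading, but not stated) and that the operator has seen every earlier paper. These counts measure possible knowledge, not bias.

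**5. Time cost of a later draw.** Surgical Procedures gives spins of 8-12 minutes (PRF) and 12-14 minutes (A-PRF). If the whole spin now overlaps drilling, moving it adds between 8 × 8 + 8 × 12 = 160 and 8 × 12 + 8 × 14 = 208 minutes over 16 patients. Clot extraction, and blood collection if that also needs the arm, would come on top; the protocol gives no times for these.

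**The case against.** **The early draw may have a practical reason.** Materials lists separate PRF and A-PRF tubes, and the spins differ in speed and time. The spin therefore needs the arm, and blood collection may need it too. Surgical Procedures never says when blood is taken or spun; its order may be by topic. A draw straight after extraction would let preparation run during drilling. This stands. It is why the draw is a secondary point here, and the draw time contradicts no other section.

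**The bias is speculative.** The protocol gives no reason why an operator would drill or seat differently for one of two autologous clots, and both arms follow the same manufacturer's instructions. That the operator sees the paper is inferred from the absence of any statement to the contrary. This also stands. A reader might infer that the early draw breaks the randomisation, or that torque and ISQ are in fact biased. The documents support neither: the lottery itself is unaffected, and no size of shift can be derived.

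**The torque comparison only asks a question.** The section proposes to evaluate, and does not commit to a claim of benefit; torque is also one of several measures. This limits the damage but does not remove the error, because torque taken at step 4 cannot answer the question.

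**Conclusion.** The Insertion torque section is wrong as written. Torque is recorded before the filler is applied, so an arm difference cannot be evidence about the preparations. This needs no assumption about operator behaviour. It rests only on the filler going in after the implant is seated, as Surgical Procedures lists it and Study Design implies. If practice differs, the protocol must say so.

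The time of the draw is a weakness worth a cheap improvement, and no more than that. The arm can be known before torque in up to all 16 patients, against about 1.8 on average with a later draw under the assumptions above. Whether that knowledge alters placement is not shown. Carry-over into ISQ would be a further step of unknown size.

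**What to change.** 1. **Insertion torque (main change).** Replace the comparative paragraph with wording such as: *Insertion torque will be summarised by group as a baseline description of implant placement. It will not be used to judge the effect of either preparation on initial stability.* This costs a sentence and nothing else.

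2. **Randomization (where workflow allows).** Have the paper drawn after the implant is seated and torque is recorded; torque then becomes a true pre-allocation baseline. Otherwise keep the draw where it is and keep the paper from the operator until torque is recorded, if existing staff can run the preparation. Because the patient draws a paper that names the procedure, this second option needs a stated handling step.

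**Cost of the second change.** If preparation already follows seating, as Surgical Procedures lists it, a later draw adds almost nothing. If preparation now overlaps drilling, it adds the spin of 8-12 or 12-14 minutes per patient, plus clot extraction, plus blood collection if that needs the arm, all with the site not yet sutured. The investigators have to weigh that wait. Withholding the paper avoids it but needs a second person. Under either option the last papers may be guessed by elimination. The sample stays at 16 and no measurement is added.
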